13.2. Planned Statistical Analysis

The main objective of the statistical analysis will be to estimate the effect of Pioglitazone on the occurrence of skin tumors when used in combination with usual care compared to usual care alone. The primary endpoint will be the total number of skin tumors counted during each treatment period. We will have two observations per patient, one for each treatment period of the 2-by-2 cross-over design (either baseline to 6 months, or 6 months to 12 months post-baseline). We will first compute the empirical mean (and its standard error), standard deviation and median for the number of skin tumors within each treatment arm and each treatment period. We will also construct histograms for tumor counts. We expect tumor counts to range between 0 and 6 per six months, such that parametric mixed analysis of variance (ANOVA) may not be the most appropriate approach to assess treatment effects. As an alternative, we will describe the number of skin tumors using log-linear Poisson regression models with random effects. The developed models will include treatment arm, period, and their interaction as covariates while adjusting for potential intra-subject dependencies (or between subject variation) using random intercepts. We will use this model to investigate the presence of washout effect (secondary aim).

In additional, exploratory analyses, we will assess if the phenotype of skin tumors changes during treatment with Pioglitazone. We will also determine if Pioglitazone changes the expression of markers influenced by PPAR γ or AKR1C3 (apoptosis, proliferation) in tumors removed from treated patients. We will have an apoptosis and a proliferation score for every skin tumor that arises, both treated as continuous variables. The analyses will be conducted using mixed ANOVA modeling the apoptosis and the proliferation scores of each tumor as a function of treatment arm,

period, and their interaction. Random intercepts will also be included in the models to account for subject to subject variability. We will develop separate models for the apoptosis and for the proliferation scores. We will investigate modeling assumptions using plots of residuals and conditional residuals. In the event modeling assumptions appear violated, we will consider applying suitable transformations (e.g., logarithmic, square root) to normalize the data. As an alternative, we will consider performing statistical inference using a generalized estimating equations (GEE) approach.

All tests and construction of confidence intervals will be two-sided and conducted at the 5% significance level.

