2.2. Rationale for Study Design

An open label study with a crossover design was selected because this is a feasibility pilot project funded by the Department of Dermatology, and we require a study design that can yield useful statistical information for sample size for a subsequent multi-center trial with the number of subjects we are likely able to recruit here at Rochester. We calculate that 40 patients will be needed to provide the sample size required to determine a statistically significant drug effect for a larger study. We also expect that it may not be possible to identify and enroll more high risk patients at Rochester in a reasonable period of time given the incidence of multiple SCC and the eligibility criteria. It is possible this design may not give a long enough period of time on drug to substantially decrease the onset of new tumors, however we believe it will be sufficient since 2 other drugs that affect the frequency of SCC in susceptible patients do produce substantial effects in this time frame (Celebrex, Soriatane)(Elmets *et al.*, 2010; Kadakia *et al.*, 2012). A one year long study will permit completion of a feasibility pilot in a reasonable period to allow a larger, definitive study to be done. We hypothesize that Pioglitazone will have the capacity to reduce incidence of SCC by >50%, as >90% decrease in growth is seen in tissue culture of human SCC using levels of pioglitazone available in human serum (see preliminary data, above). This is also the effect size seen with Celebrex treatment, a drug that can also selectively modulate prostaglandin synthesis.

We have chosen tumor incidence as the primary outcome measure. Because patients with high tumor risk develop new tumors at a variable pace, some subjects may not have any new tumors during the period of the study. However, in aggregate we feel that a tumor endpoint is the best choice. This decision was made because of our recent experience studying the effects of Celebrex on skin cancer incidence. That study assessed pre-skin cancers (actinic keratoses) as the primary endpoint(Elmets *et al.*, 2010). However, when data was analyzed, it was found there was no significant change in precursor lesions, only in actual tumor numbers. Thus, we have elected to focus on a high risk population that will have high numbers of new tumors. These patients are also the target group that could derive the most benefit from treatment.

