13. DATA ANALYSIS AND MONITORING

13.1. Sample Size Determination

[figure not shown]
This pilot study will be designed as a 2-by-2 crossover trial. We refer to Section 2.2 for a justification of the study design. Patients will be enrolled and randomized in one arm of two treatment protocols. Each protocol will include two treatments administered during two consecutive time periods:

- Treatment arm # 1: Patients enrolled in the first arm will first receive six months of usual care (*Period 1*); next, they will be treated with Pioglitazone combined with usual care for the next 6 months (*Period 2*). Patients will take study drug until they come to their final “on Treatment” visit, which will occur 168 days +/- 14 days of their “on Treatment” date.
- Treatment arm # 2: Patients enrolled in the second arm will first receive six months of Pioglitazone treatment combined with usual care (*Period 1*); next, they will receive usual care alone during the following 6 months (*Period 2*). Patients will take study drug until they come to their final “on Treatment” visit, which will occur 168 days +/- 14 days of their “on Treatment” date.

A flow diagram describing the study design is presented in Section 2.

The primary endpoint will be the total number of skin tumors counted during each treatment period. Based on clinical evidence, we expect the total number of skin tumors to range between 0 and 3 per patient and per treatment period (or 0 to 6 per patient per year) and to average around 1.5. We would consider Pioglitazone to be clinically effective if it reduces tumor counts by 50% (that is, reduce the average number of tumors from 1.5 to 0.75 per patient and per treatment period). Previous work by this investigator has shown that such reductions in tumor numbers can occur when prostaglandin metabolism is affected by drug treatment (Elmets *et al.*, 2010).

A two-sided *t*-test achieves 96% power to detect a reduction in the number of skin tumors due to Pioglitazone when the total sample size of a 2-by-2 crossover design is 40 (20 patients per group). The calculations assumed that the actual mean difference is 0.75 (corresponding to a 50% reduction in the mean number of skin tumors due to treatment), the square root of the within mean square error is 1, and the significance level is 5%. The figure below displays the power of the study as a function of the sample size (N) for three values of the square root of the within mean square error (SW).

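### Cheap improvement: the primary Poisson model fixes the within-patient variance at its Poisson value, so its interval and p-value have no protection if counts vary more than that between a patient's two periods

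*Combined protocol and SAP*

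**What the plan says.** Section 13.2 sets mixed ANOVA aside because the counts are small and will instead "describe the number of skin tumors using log-linear Poisson regression models with random effects". On the fixed part: "The developed models will include treatment arm, period, and their interaction as covariates". On dependence, the model works by "adjusting for potential intra-subject dependencies (or between subject variation) using random intercepts". The data are two counts per patient: "We will have two observations per patient, one for each treatment period of the 2-by-2 cross-over design". On error rates: "All tests and construction of confidence intervals will be two-sided and conducted at the 5% significance level".

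For the tumor count, 13.2 names no dispersion parameter, negative binomial form, patient-by-period effect or robust variance. Standard deviations and histograms will be produced by arm and period, but no action depends on them. Later in 13.2 come residual plots, transformations and the statement that "we will consider performing statistical inference using a generalized estimating equations (GEE) approach". These follow directly on the models for apoptosis and proliferation scores and speak of normalizing data, so on a plain reading they do not reach the tumor count.

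Section 13.1 bases power on a two-sided t-test with 40 patients, a mean difference of 0.75 and a within-patient standard deviation (Sw) of 1.

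**The concern.** A t-test or ANOVA estimates within-patient error from the data. A Poisson model with only a random intercept does not: it absorbs differences between patients, then takes the variance from one period to the next as equal to the mean. So in moving from the t-test of 13.1 to the model of 13.2, the plan gives up a variance that the data could have corrected, and does not say so.

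At stake are the width of the primary confidence interval and the calibration of the primary p-value. The pilot's main use is to plan a larger trial. Within-patient dispersion is an input to that plan, and the stated model assumes it instead of estimating it.

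**Working it through.** **Inputs from the documents.** 20 patients per sequence; means of 1.5 (usual care) and 0.75 (pioglitazone) per period; Sw = 1; two-sided 5% (13.1 and 13.2).

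**Assumed, because the documents give no figure.** Stable patient frailty is gamma with variance 0 to 0.5. Extra within-patient variation phi runs from 0 to 1, so that variance = mean × (1 + phi × mean). At mean 1.5, phi of 0.1, 0.25, 0.5 and 1 gives a variance-to-mean ratio of 1.15, 1.375, 1.75 and 2.5.

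**The plan's own power figure.** SE = Sw × √(2/N) = 1 × √(2/40) = 0.2236, and 0.75/0.2236 = 3.354. Two-sided power is 90.5% (noncentral t, 38 df) or 91.8% (normal), against the stated 96%. That mismatch is a separate matter, and nothing below depends on it.

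**What Sw = 1 implies.** Within-patient variance is 1² = 1.0. Poisson would give (1.5 + 0.75)/2 = 1.125 with the planned effect, or 1.5 with none. The planning value therefore implies no overdispersion.

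**Standard error under the planned model.** With arm, period and their interaction all fitted, the likelihood splits into patient totals, which carry the intercept, and within-patient splits between periods, which carry treatment. The standard error of the log rate ratio is

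SE = 0.5 × √(1/S₁ + 1/S₂ + 1/S₃ + 1/S₄),

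where S₁ to S₄ are the four arm-by-period tumor totals. The intercept variance does not appear. Fitting the mixed model by quadrature to three simulated datasets gave the same estimates and standard errors to at least six decimals.

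With no drug effect each S is about 20 × 1.5 = 30, so SE ≈ 0.5 × √(4/30) = 0.183, whatever phi is.

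**Rough size by hand.** With no frailty, the true variance is larger by the factor 1 + 1.5 × phi. At phi 0.5 that is 1.75. The 1.96 cut-off then acts as 1.96/√1.75 = 1.48, a two-sided error of about 14%.

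**Simulation, no drug effect** (40,000 trials per setting; each pair is frailty variance 0 / 0.5):

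| phi | Mean model SE | True SE | Planned test rejects | t-test on period differences rejects |
|---|---|---|---|---|
| 0 | 0.186 / 0.188 | 0.187 / 0.189 | 4.8% / 4.8% | 4.8% / 4.8% |
| 0.1 | 0.186 / 0.188 | 0.201 / 0.211 | 6.5% / 7.6% | 4.9% / 4.9% |
| 0.25 | 0.187 / 0.190 | 0.221 / 0.236 | 9.4% / 11.2% | 5.0% / 4.9% |
| 0.5 | 0.188 / 0.191 | 0.250 / 0.275 | 13.6% / 16.5% | 4.9% / 4.7% |
| 1 | 0.190 / 0.195 | 0.298 / 0.341 | 20.6% / 25.7% | 4.8% / 4.5% |

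At phi 0.5 and frailty 0.5 the model's SE is 1 − 0.191/0.275 ≈ 30% too small. The first row shows that stable differences between patients do not disturb the test.

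**Robust alternative.** Patient-clustered errors with the variance multiplied by (20/19)² and a t(38) reference reject 4.3–6.0% up to phi 0.5 and at most 6.8% at phi 1. Without the correction they are somewhat liberal, at 4.8–7.6% in the same settings.

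**Cost if counts are exactly Poisson** (rate ratio 0.5). The planned test has 88–89% power, corrected robust errors 85–86%, and the t-test 86–88%.

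**The case against.** The strongest reply is that nothing in the documents shows this trial has the harmful kind of variation. That stands. Three stronger readings are tempting, and the documents support none of them.

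- **Variable pace.** Section 2.2 says "Because patients with high tumor risk develop new tumors at a variable pace", some subjects may have no tumors. A reader might take this as evidence of within-patient clumping. It more naturally describes differences between patients, and section 5.1 attributes the variability to the predisposing condition. The random intercept absorbs that.
- **Biopsies at visits.** A reader might infer that finding several tumors at one visit overdisperses the count. The endpoint is a six-month total, and a Poisson process detected in batches still has a Poisson total. Tumors would have to arise in batches, which the documents do not say.
- **A biased effect.** The log rate ratio comes from the four arm-by-period totals and is the same with model-based or robust errors. The estimate carried into the larger trial does not move.

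Sw = 1 also points away from overdispersion. The range of 0 to 3 tumors per period in 13.1, with a mean of 1.5, caps the total variance at (3/2)² = 2.25, a ratio of 1.5, so the larger phi values conflict with it. Section 13.2, however, expects 0 to 6 per six months, which leaves more room. The two ranges show that the spread is not settled.

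Finally, this is a feasibility pilot whose stated aim is estimation, so type I error matters less than in a confirmatory trial. That lowers the urgency, but an interval that is too narrow is also a fault in estimation. If the GEE option was meant to cover tumor counts, with robust variance, most of the concern would go; the text would need to say so.

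**Conclusion.** The concern holds as a conditional statement and a cheap improvement. The gap in the model is certain: the planned standard error for treatment cannot respond to extra-Poisson variation within patients. Whether that variation is present is unknown.

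If it is absent, the planned test is sound, at just under 5%. If it is present, the false-positive rate is about 7% at phi 0.1, 9–11% at 0.25, 14–17% at 0.5 and 21–26% at 1, given 20 per arm, mean 1.5 and frailty variance 0 to 0.5. These are results over assumed values, not a forecast for this trial. It would go too far to say that the primary test is inflated as planned.

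**What to change.** Change the wording of 13.2 for the primary count:

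1. Keep the log-linear model for the rate ratio. Take the primary interval and p-value from patient-clustered robust errors with a small-sample correction and a t(38) reference. Alternatively, take the p-value from the t-test on within-patient period differences, which matches the power calculation in 13.1 and is the better calibrated of the two. Name one as primary.
2. Report the estimated within-patient dispersion, for use in planning the larger trial.
3. Name a negative binomial mixed model as the sensitivity analysis.
4. State whether the residual checks and GEE option apply to tumor counts.

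No change to conduct, data or sample size is needed. If counts are exactly Poisson, corrected robust errors cost about 2–3 points of power (88–89% to about 86%), and the t-test 1–2 points.

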3.2. Inclusion and Exclusion Criteria

a) Inclusion Criteria:

- >18 years of age, male or female, state of health stable
- Able understand protocol and give consent
- Has had treatment of 2 – 6 squamous cell carcinomas of the skin during the year prior to enrollment, & pathology is available for verification
- Stable treatment regimen for their skin cancer problems in place for 1 year, with expectation to keep medications the same during study
- Able to keep study appointments & comply with protocol

b) Exclusion Criteria:

- Unwillingness or unable to complete informed consent process
- < 18 years of age
- Allergy to Pioglitazone
- Taking Rifampin, Trimethaprim, Celebrex or Gemfibrozil
- Pregnant or breastfeeding (Pregnancy Category C)
- History of heart failure NYHA Class III or Class IV
- Subjects with type 1 or type 2 diabetes
- Problems with pedal edema
- Liver disease (ETOH, viral hepatitis, drug-induced hepatitis) or elevated ALT, AST or total bilirubin
- Osteoporosis with high risk of fracture
- History of bladder cancer
- Recent change in chronic oral medications. Participants enrolled while on a systemic medication for their skin cancer must remain on treatment.

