5.1. Efficacy Assessments

Administration of Pioglitazone to prevent/decrease the aggressive phenotype of skin cancer is experimental. NB- obtaining biopsy of lesions suspected of skin cancer is NOT experimental; it is required for usual patient care in these high risk patients. In order to know whether Pioglitazone is efficacious for preventing SCC in high risk individuals, we will count the number of skin tumors documented by biopsy/treatment that occur in our subjects before, during, or after Pioglitazone treatment. This assessment will take into account compliance, as described below. The tumor counts will be best interpreted in aggregate for the whole sample group, since there is variability in the frequency with which new tumors appear based on the predisposing condition. Since Pioglitazone has been on the market for some time without observation of a negative impact on skin or wound healing, the study focus will be determining if numbers of tumors decrease and whether their phenotype changes. The physician reading the pathology of the skin biopsies will be responsible for identifying the number of tumors that occur –i.e., some lesions thought to be tumors and therefore biopsied in clinical practice turn out to be hypertrophic actinic keratosis (not tumors). These would not be counted as skin cancers, since they are precancerous lesions.

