8.3. Subject Enrollment/Randomization

Subjects will be randomized to one of two study groups: initial observation or initial drug treatment followed by washout.

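### The washout test compares two different groups of 20 patients, yet its model leaves out the prior-year SCC count that every patient has at entry

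*Combined protocol and SAP*

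**What the plan says.** Section 13.2 plans a log-linear Poisson regression of six-month tumor counts: "The developed models will include treatment arm, period, and their interaction as covariates", with random intercepts for patients. On persistence after stopping drug it says: "We will use this model to investigate the presence of washout effect (secondary aim". No baseline covariate is named in 13.2.

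Section 13.1 sets the size: "the total sample size of a 2-by-2 crossover design is 40 (20 patients per group"). Section 8.3 says only "Subjects will be randomized to one of two study groups"; no stratification is described.

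The inclusion criterion in Section 3.2 reads "Has had treatment of 2 – 6 squamous cell carcinomas of the skin during the year prior to enrollment", with pathology required for verification. Section 3.4 explains that enough prior tumors are required for the raised future risk to be evident.

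**The concern.** The drug effect is estimated within patients, so stable differences in tumor rate cancel. Persistence after stopping is different. It asks whether usual care after drug differs from usual care never preceded by drug, and only arm 1 supplies the latter. Patient differences therefore stay in the answer.

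Entry allows a three-fold range of prior-year counts (6/2 = 3). If the arms of 20 differ by chance on that count, part of the difference passes into the washout estimate. The plan does not say in advance what it would do then, and adjusting after seeing the imbalance would be post hoc.

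**Working it through.** **The plan's own figure.** Section 13.1 states that the t-test "achieves 96% power to detect a reduction in the number of skin tumors due to Pioglitazone", assuming "the actual mean difference is 0.75", a within-patient SD of 1 and a 5% level. For a 2-by-2 crossover the noncentrality is 0.75 / (1 × √(2/40)) = 3.354 on 38 df. That gives 90.5% two-sided and 95.0% one-sided, so 96% does not reproduce as a two-sided figure. This is a separate matter: it concerns the drug effect, and the plan gives no power or precision for washout.

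**1. Where carryover sits in the model.** On the log scale let m be usual care, p period, t drug and c carryover.

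| | Period 1 | Period 2 |
|---|---|---|
| Arm 1 (usual care first) | m | m + p + t |
| Arm 2 (drug first) | m + t | m + p + c |

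- Arm term = (m + t) − m = t.
- Interaction = (p + c − t) − (p + t) = c − 2t.
- Hence c = interaction + 2 × arm term, which is the arm 2 sum minus the arm 1 sum.

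This is wholly a between-group contrast. The within-patient drug estimate, minus half the interaction when c = 0, is not.

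**2. Its standard error.** Take a usual-care mean of 1.5 and 0.75 on drug (13.1), full persistence (0.75 after drug) and 20 per arm. If patient rates have coefficient of variation CV and covariates explain a share R² of their variance:

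Var(c) ≈ (1/20)(1/1.5 + 3/0.75) + (8/20) CV² (1 − R²) = 0.233 + 0.4 CV² (1 − R²)

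- CV 0.5, R² 0: √(0.233 + 0.100) = 0.577. The effect is ln 0.5 = −0.693, so z = 1.20 and power is 22%.
- CV 1.0, R² 0: √(0.233 + 0.400) = 0.796, power 14%.

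A covariate can act only on the second term.

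**3. What the prior count buys.** The documents give neither CV nor R², so both are assumptions. The planned random-intercept model was fitted to simulated trials (gamma-distributed rates, entry restricted to 2–6, full persistence, 600 runs each). CV here is that of the population before the entry restriction.

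| Population CV | Rate variance explained by prior count | SE without → with | Power without → with |
|---|---|---|---|
| 0.3 | 10% | 0.512 → 0.514 | 28% → 29% |
| 0.5 | 18% | 0.533 → 0.525 | 27% → 28% |
| 1.0 | 29% | 0.572 → 0.541 | 20% → 24% |

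With no true carryover and CV 1.0 the SE goes from 0.550 to 0.516, a fall of 6%. The drug-effect SE (0.22–0.24) is the same with and without the covariate.

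**4. What it buys when the arms differ.** Because c adds the arm difference over two periods, a log-rate difference D between arms shifts the estimate by 2D. A 20% difference carried through in full would give 2 × ln 1.2 = 0.36. Prior count is a noisy measure of the true rate, so the amount carried depends on CV.

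With no true carryover and CV from 0.3 to 1.4, mean prior counts differ by more than 20% in 11–16% of randomizations. In those, the unadjusted estimate shifts by 0.08–0.43 on average and the adjusted one by about zero. If arm 2 has the lower counts, 0.1 to 0.4 reads as a spurious persistent reduction of 10% to 33% (1 − e^−0.1 to 1 − e^−0.4). Even 0.4 is below one standard error (0.4/0.57 = 0.7).

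**The case against.** The strongest reply is that the arms are randomized and the model has a random intercept, so chance imbalance is ordinary sampling error already reflected in the standard error. The gain is close to nil in two of the three scenarios, washout is a secondary aim of a feasibility pilot, and the binding limit is 20 against 20. All of this stands. It limits the size of the point but does not remove it: averaged over randomizations the estimate is unbiased, but given a visible imbalance it shifts, and the plan prespecifies no response. Withdrawn subjects are also replaced (Section 7), so the groups finally compared need not be exactly those randomized.

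It is also fair that arm 2's change from on-drug to off-drug is within-patient and bears on the Section 1.1 question of whether cancers return. That change equals p + c − t, however, so isolating persistence still needs arm 1.

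A reader might infer more than the documents support:

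- **That the comparison in Section 2.1 of arm 1's first-period tumors with on-treatment tumors has the same weakness.** That comparison is of tumor characteristics, not counts, and on-treatment tumors include arm 1's own second period.
- **That predisposing condition should be adjusted for as well.** Section 5.1 says "there is variability in the frequency with which new tumors appear based on the predisposing condition", but the documents do not list it as a recorded variable or quantify its effect.
- **That precision can be judged from arm 2's second period against arm 1's first.** At CV 0.5 that SE is √(0.100 + 0.025) = 0.35, not 0.58, but it assumes no period effect, and the planned model includes period.
- **That randomization must be stratified.** Nothing in the documents supports a particular cut of the prior count, and blocked strata in an open-label trial of 40 could make assignments predictable.

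**Conclusion.** The point holds as one of modest size about precision and chance imbalance, for the secondary washout aim only. The carryover contrast is between patients, and a baseline count held for every patient is left out of its model.

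The SE changes by about 0 to 6%. The larger benefit is protection in the 11–16% of randomizations where mean prior counts differ by more than 20%, where an unadjusted shift of about 0.1–0.4 falls to about zero. These sizes rest on assumed gamma-distributed rates with CVs of 0.3 to 1.4.

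A reader might conclude that the washout analysis is biased or invalid, or that adjustment would rescue it. Neither follows. Randomization and the random intercept keep it valid, and power stays at roughly 14–29% with or without the covariate. The within-patient drug effect is unaffected.

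**What to change.** In Section 13.2, prespecify log(prior-year SCC count) as a fixed covariate in the random-intercept Poisson model. The count is at least 2 by eligibility, so the log is always defined.

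The cost is one sentence and one degree of freedom. No new data are needed, because the count is already established for eligibility. Since power remains low, the washout result is best read as an estimate with its confidence interval.
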